8.6. Hospitalization

Adverse events reported from studies associated with hospitalization or prolongations of hospitalization are considered serious. Any initial admission (even if less than 24 hours) to a healthcare facility meets these criteria. Admission also includes transfer within the hospital to an acute/intensive care unit (eg, from the psychiatric wing to a medical floor, medical floor to a coronary care unit, neurological floor to a tuberculosis unit).

Hospitalization does not include the following:

- Rehabilitation facilities;
- Hospice facilities;

- Respite care (eg, caregiver relief);
- Skilled nursing facilities;
- Nursing homes;
- Routine emergency room admissions;
- Same day surgeries (as outpatient/same day/ambulatory procedures).

Hospitalization or prolongation of hospitalization in the absence of a precipitating, clinical adverse event is not in itself a serious adverse event. Examples include:

- Admission for treatment of a preexisting condition not associated with the development of a new adverse event or with a worsening of the preexisting condition (eg, for work-up of persistent pre-treatment lab abnormality);
- Social admission (eg, subject has no place to sleep);
- Administrative admission (eg, for yearly physical exam);
- Protocol-specified admission during a study (eg, for a procedure required by the study protocol);
- Optional admission not associated with a precipitating clinical adverse event (eg, for elective cosmetic surgery);
- Pre-planned treatments or surgical procedures should be noted in the baseline documentation for the entire protocol and/or for the individual subject.

Diagnostic and therapeutic non-invasive and invasive procedures, such as surgery, should not be reported as adverse events. However, the medical condition for which the procedure was performed should be reported if it meets the definition of an adverse event. For example, an acute appendicitis that begins during the adverse event reporting period should be reported as the adverse event, and the resulting appendectomy should be recorded as treatment of the adverse event.

8.7. Severity Assessment

Table 3. Severity Assessment

If required on the adverse event case report forms, the investigator will use the adjectives MILD, MODERATE, or SEVERE to describe the maximum intensity of the adverse event. For purposes of consistency, these intensity grades are defined as follows:	
MILD	Does not interfere with subject's usual function.
MODERATE	Interferes to some extent with subject's usual function.
SEVERE	Interferes significantly with subject's usual function.

Note the distinction between the severity and the seriousness of an adverse event. A severe event is not necessarily a serious event. For example, a headache may be severe (interferes significantly with subject's usual function) but would not be classified as serious unless it met one of the criteria for serious adverse events, listed above.

8.8. Causality Assessment

The investigator's assessment of causality must be provided for all adverse events (serious and non-serious); the investigator must record the causal relationship in the CRF, as appropriate, and report such an assessment in accordance with the serious adverse reporting requirements if applicable. An investigator's causality assessment is the determination of whether there exists a reasonable possibility that the investigational product caused or contributed to an adverse event. If the investigator does not know whether or not investigational product caused the event, then the event will be handled as "related to investigational product" for reporting purposes, as defined by the Sponsor (See Section on Reporting Requirements). If the investigator's causality assessment is "unknown but not related to investigational product", this should be clearly documented on study records.

In addition, if the investigator determines a serious adverse event is associated with study procedures, the investigator must record this causal relationship in the source documents and CRF, as appropriate, and report such an assessment in accordance with the serious adverse event reporting requirements, if applicable.

8.9. Exposure During Pregnancy

This is a study exclusively in pregnant women participants. Enrolled subjects will be asymptomatic pregnant women who will receive study drugs for preventive treatment of malaria. Since this is the first time AZ and CQ combination will be administered to pregnant women, all subjects will be followed up for EIU safety assessments following delivery or termination of pregnancy. The reason(s) for an induced abortion should be specified. All pregnancy-related AEs through Day 42 following the first dose of AZCQ and the pregnancy outcomes will be recorded on CRF pages as required clinical study data. Since all the information generally included on an EIU form will be collected on CRF paper, a separate EIU form is not required.

090177e1811d3ccb\Approved\Approved On: 19-Feb-2010 20:59

If the outcome of the pregnancy meets the criteria for immediate classification as a serious adverse event (ie, spontaneous abortion, stillbirth, neonatal death, or congenital anomaly [including that in an aborted fetus, stillbirth or neonatal death]), the investigator should follow the procedures for reporting serious adverse events.

In the case of a live birth, the “normality” of the newborn can be assessed at the time of birth (ie, no minimum follow-up period of a presumably normal infant is required before an Exposure in Utero Form can be completed). The “normality” of an aborted fetus can be assessed by gross visual inspection, unless pre-abortion test findings are suggestive of a congenital anomaly.

Additional information about pregnancy outcomes that are classified as serious adverse events follows:

- “Spontaneous abortion” includes miscarriage and missed abortion.
- All neonatal deaths that occur within 1 month of birth should be reported, without regard to causality, as serious adverse events. In addition, any infant death after 1 month that the investigator assesses as possibly related to the exposure during pregnancy to the investigational medication should be reported.

Additional information regarding the EIU may be requested by the investigator. Further follow-up of birth outcomes will be handled on a case-by-case basis (eg, follow-up on preterm infants to identify developmental delays). In the case of paternal exposure, the investigator must obtain permission from the subject’s partner in order to conduct any follow-up or collect any information.

8.10. Withdrawal Due to Adverse Events (See also Section on Subject Withdrawal)

Withdrawal due to adverse event should be distinguished from withdrawal due to insufficient response, according to the definition of adverse event noted earlier, and recorded on the appropriate adverse event CRF page.

When a subject withdraws due to a serious adverse event, the serious adverse event must be reported in accordance with the reporting requirements defined below.

Unless a subject withdraws consent or leaves the town/village, she may be withdrawn from the study treatment but should continue in the study as we must follow them up for pregnancy outcome.

8.11. Eliciting Adverse Event Information

The investigator is to report all directly observed adverse events and all adverse events spontaneously reported by the study subject. In addition, each study subject will be questioned about adverse events.

090177e1811d3ccb\Approved\Approved On: 19-Feb-2010 20:59

8.12. Reporting Requirements

Each adverse event is to be assessed to determine if it meets the criteria for serious adverse events. If a serious adverse event occurs, expedited reporting will follow local and international regulations, as appropriate.

8.12.1. Serious Adverse Event Reporting Requirements

If a serious adverse event occurs, Pfizer is to be notified within 24 hours of awareness of the event by the investigator. In particular, if the serious adverse event is fatal or life-threatening, notification to Pfizer must be made immediately, irrespective of the extent of available adverse event information. This timeframe also applies to additional new information (follow-up) on previously forwarded serious adverse event reports as well as to the initial and follow-up reporting of Exposure during pregnancy cases.

This timeframe of reporting within 24 hours also applies for the reporting of any medical device complaint.

In the rare event that the investigator does not become aware of the occurrence of a serious adverse event immediately (eg, if an outpatient study subject initially seeks treatment elsewhere), the investigator is to report the event within 24 hours after learning of it and document the time of his/her first awareness of the adverse event.

For all serious adverse events, the investigator is obligated to pursue and provide information to Pfizer in accordance with the timeframes for reporting specified above. In addition, an investigator may be requested by Pfizer to obtain specific additional follow-up information in an expedited fashion. This information may be more detailed than that captured on the adverse event case report form. In general, this will include a description of the adverse event in sufficient detail to allow for a complete medical assessment of the case and independent determination of possible causality. Information on other possible causes of the event, such as concomitant medications and illnesses must be provided. In the case of a subject death, a summary of available autopsy findings must be submitted as soon as possible to Pfizer or its designated representative.

In addition, the Investigator will follow all applicable local and national safety reporting guidelines and regulations for notification to their local ethics and regulatory bodies.

8.12.2. Non-Serious Adverse Event Reporting Requirements

All adverse events will be reported on the adverse event page(s) of the CRF. It should be noted that the form for collection of serious adverse event information is not the same as the adverse event CRF. Where the same data are collected, the forms must be completed in a consistent manner. For example, the same adverse event term should be used on both forms. Adverse events should be reported using concise medical terminology on the CRFs as well as on the form for collection of serious adverse event information.

8.12.3. Medical Device Complaint Reporting Requirements

Not applicable.

8.12.4. Sponsor Reporting Requirements to Regulatory Authorities

Adverse events reporting, including suspected serious unexpected adverse reactions, will be carried out in accordance with applicable local regulations.

9. DATA ANALYSIS/STATISTICAL METHODS

Detailed methodology for summary and statistical analyses of the data collected in this trial will be documented in an Analysis Plan, which will be dated and maintained by the Sponsor. This document may modify the plans outlined in the protocol; however, any major modifications of the primary endpoint definition and/or its analysis will also be reflected in a protocol amendment.

An early analysis of the data will be performed on parasite related endpoints (up to Day 42), including the primary, when all subjects achieve their Day 42 visit (ie, 42 days of follow-up post first dose), or withdraw from the study early.

9.1. Sample Size Determination

There will be approximately 166 subjects in the study. This will be a single arm, non-comparative estimation study and will not be powered for formal hypothesis testing. The sample size will yield a half width of a 2-sided 95% confidence interval to be ≤ 5 percentage points with probability=0.80 for the primary efficacy endpoint, using a large sample normal approximation to the binomial provided the true underlying incidence is $\geq 95\%$, and assuming approximately 10% will drop out.

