Approximately 166 subjects will be enrolled in the study. Since this is a supportive study to understand one of the possible mechanisms for IPTp effect, it is not powered for formal hypothesis testing. The sample size will yield a half width of a 2-sided 95% confidence interval (CI) to be ≤ 5 percentage points with probability=0.80 for the primary efficacy endpoint, using a large sample normal approximation to the binomial, provided the true underlying incidence is $\geq 95\%$, and assuming approximately 10% will drop out.

Independent Data Monitoring Committee (IDMC)

The IDMC constituted for IPTp will review safety data at regular intervals to be determined at the time of DMC charter development.

Study Schematic

090177e1811d3ccb\Approved\Approved On: 19-Feb-2010 20:59

SCHEDULE OF ACTIVITIES

Protocol Activity	Treatment			Follow Up Visits						
	Day 0 ^a	Day 1	Day 2	Day 7	Day 14	Day 21	Day 28	Day 35	Day 42	At/Post Delivery ^b
Informed Consent Process	X									
Medical History	X									
Obstetrical History	X									
Concomitant Treatment History	X	X	X	X	X	X	X	X	X	X
Rapid Diagnostic Test (eg, Binax)	X									
Complete Physical Exam	X									
Limited Physical Exam									X	
Oral Temperature	X	X	X	X	X	X	X	X	X	
Routine Obstetric checkup	X									
Ultrasound ^c	X									
Laboratory										
Peripheral Blood Smears ^d	X			X ^d	X ^d	X ^d	X ^d	X ^d	X ^d	
Hemoglobin (Hb)	X								X	
Urine Pregnancy Test ^e	X									
Urine Test for Glucose & Protein	X									
Blood Blot for Molecular Testing										
Molecular Genotyping for P. Falciparum ^f	X			X ^f	X ^f	X ^f	X ^f	X ^f	X ^f	
Genetic Marker for CQ Resistance	X									
Administer Treatment Azithromycin-Chloroquine (AZCQ ^g)	X	X	X							
Distribute Long lasting insecticidal-treated bednets (LLITs)	X									
Confirm the Installation of LLINs at Home by Fieldworkers		X								
Blood Samples for AZ, CQ and desethyl-CQ Analysis ^h	X ⁱ		X ^j	X ^k	X ^k	X ^k	X ^k			
Adverse Events Assessment	X	X	X	X	X	X	X	X	X	
Exposure in Utero (EIU) Assessment ^l										X

090177e1811d3ccb\Approved\Approved On: 19-Feb-2010 20:59

- ^a All tasks should be performed prior to the first dose except AE assessment and bednet distribution.

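### The 0.80 in the sample size statement does not belong to the quantity it describes: 166 women give a half width of at most 5 points with probability about 0.999

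*Protocol*

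**What the plan says.** Section 9.1 (Sample Size Determination) fixes every input. It says "There will be approximately 166 subjects in the study" and describes a "single arm, non-comparative estimation study and will not be powered for formal hypothesis testing". The precision target is a "half width of a 2-sided 95% confidence interval to be ≤ 5 percentage points with probability=0.80 for the primary efficacy endpoint", obtained "using a large sample normal approximation to the binomial", on condition that the true rate is 95% or more and "assuming approximately 10% will drop out". The synopsis, under Number of Subjects, repeats it: "The sample size will yield a half width of a 2-sided 95% confidence interval (CI) to be ≤ 5 percentage points with probability=0.80".

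The analysis itself (section 9.2.1) estimates the Day 28 response from a Kaplan-Meier curve with a Greenwood standard error, so the binomial calculation is a planning approximation.

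**The concern.** In an estimation study without a hypothesis test, this sentence is the only quantitative justification of the sample size. A reader who takes the stated inputs and computes the stated probability does not get 0.80 or anything near it. As written, the sentence implies a one in five chance that the interval will be wider than plus or minus 5 points. Under the protocol's own assumptions that chance is about one in 750 (1 / 0.0013). Ethics committees and regulators who check the number will find that it fails, and other readers will misjudge how precise the primary estimate will be.

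**Working it through.** **Inputs (all from section 9.1).** Enrolled: 166. Dropout: 10%, so 166 × 0.90 = 149.4, about 149 evaluable. True response rate: 0.95, the least favourable value allowed. Interval: two-sided 95%, normal approximation, half width = 1.96 × √(q(1 − q)/n), where q is the observed failure proportion. Target: half width ≤ 0.05 with probability 0.80.

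**Step 1: the stated probability.** With n = 149:
- 16 failures: half width 4.97 points.
- 17 failures: half width 5.10 points.

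The event is therefore 16 or fewer failures, and P(Bin(149, 0.05) ≤ 16) = 0.9987. At an observed rate of exactly 95% the half width is 1.96 × √(0.95 × 0.05/149) = 3.5 points.

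**Step 2: does another reasonable reading give 0.80?**

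| Variant, true rate 95% | P(half width ≤ 5 points) |
|---|---|
| Stated interval, n = 149, exact binomial | 0.9987 |
| Same, normal approximation for the observed rate | 0.9995 |
| Same, number of dropouts random | 0.998 |
| Stated interval, all 166 evaluable | 0.9999 |
| Wilson, n = 149 | 0.997 |
| Agresti-Coull, n = 149 | 0.997 |
| Continuity-corrected normal, n = 149 | 0.982 |
| Clopper-Pearson, n = 149 | 0.982 |

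None comes near 0.80. A true rate above 95% only raises the probability.

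**Step 3: where 166 can come from.** Put the protocol's own figures, unchanged, into the usual power-type formula:

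n = (z₀.₉₇₅ + z₀.₈₀)² × p(1 − p)/d² = (1.960 + 0.842)² × 0.95 × 0.05/0.05² = 149.1

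and 149.1/0.90 = 165.7, which rounds up to 166.

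In this formula 0.80 is the probability that the lower 95% limit is at or above 0.95 − 0.05 = 0.90 when the true rate is 0.95. Check at n = 149: the standard error is √(0.95 × 0.05/149) = 0.01785. Then 0.05/0.01785 − 1.960 = 0.840, and Φ(0.840) = 0.80. By exact binomial, the lower limit of the normal-approximation interval is at least 90% with 9 or fewer failures, which has probability 0.787.

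So the sample size is not an arithmetic slip. The 0.80 appears to be attached to the wrong quantity.

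**The case against.** **The effect is harmless.** Under its own assumptions the trial delivers a half width of at most 5 points with more than the promised probability, and no analysis, decision rule or conclusion depends on the 0.80. This stands, and it limits the weight of the point. It does not make the sentence right: the text equates the probability with 0.80 and does not say that it is at least 0.80.

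**The real analysis is Kaplan-Meier.** Section 9.2.1 also censors women who receive antimalarials for reinfection, so the effective number could fall below 149. True, and the three-decimal figures should be read with that in mind. But it does not rescue 0.80: with only 101 evaluable women the probability is still 0.87, and with 110 it is 0.90.

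**A reader might infer that too many women are enrolled.** Under the literal sentence, a probability of 0.80 is first reached at 93 evaluable women and holds for every number from 101 upward. That is about 104 to 113 enrolled, or 53 to 62 fewer than 166. This inference requires the literal sentence to have been the design target. Step 3 suggests otherwise, and the protocol does not settle it, so an excess is not shown.

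**A reader might infer that the 5 points or the 95% is misprinted.** At n = 149 the probability is 0.787 for a half width of at most 4 points at 95%, and 0.814 for at most 5 points at a true rate of 91%. Neither 4 points as a target nor 91% as an assumed rate appears in the sample size text, and the fits are loose. The 4-point target already reaches 0.80 at 143 evaluable women, and the 91% version falls below 0.80 again at 151 and 152. The lower-limit reading needs no changed input.

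**Conclusion.** The stated probability is wrong as written. On the stated inputs (149 evaluable, true rate 95%, normal approximation) it is 0.9987, not 0.80, and between 0.982 and 0.9999 under every variant tried.

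The number 166 itself is reproducible as the size that gives a lower 95% limit of at least 90% with probability about 0.80 (0.80 by normal approximation, 0.787 by exact binomial). That this was the sponsor's calculation is an inference from the exact match; the protocol does not say so.

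The error is conservative and one of description. It does not endanger the primary estimate and is no ground for changing enrolment. It should still be corrected, because nothing else in the protocol justifies the sample size numerically.

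**What to change.** Keep 166. Correct the sentence in section 9.1 and in the synopsis (Number of Subjects) in one of two ways:

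1. Keep the half-width criterion and change the probability: with about 149 evaluable women and a true rate of at least 95%, the half width of the two-sided 95% interval will be at most 5 percentage points with probability above 0.99. It would help to add that the half width at an observed rate of 95% is about 3.5 points.
2. If it was the criterion used, state that one: the lower limit of the two-sided 95% interval will be at least 90% with probability about 0.80 if the true rate is 95%.

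The sponsor should check the original calculation before choosing the second wording. The first is correct whichever formula was used. The cost is one sentence in two places, with no change to enrolment, conduct or analysis.

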9.2. Parasitological Response Analysis

Three study populations will be defined as follows.

- Intent-To-Treat (ITT): ITT is defined as all subjects who receive at least one dose of study medication and who have baseline blood smears positive for *Plasmodium falciparum* mono-infection, asexual parasitemia.
- Modified Intent-To-Treat (MITT): MITT is a subset of the ITT Population who has *Plasmodium falciparum* mono-infection (confirmed by microscopy) parasite counts in the range of 80-100,000/ μL on thick blood smears.
- Per Protocol (PP): PP is a subset of MITT subjects who receive all 3 days of study medication.

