6.1.2. Days 1 Home Visit (by the field worker)

- Assess adverse events;
- Concomitant treatment history;
- Oral temperature: will be taken by the fieldworker;
- If a subject presents with symptoms of malaria (fever $>37.5^{\circ}\text{C}$, oral), no further AZCQ dose would be given. The subject would be immediately referred to the investigator for parasite counts and appropriate treatment for malaria in pregnancy as per national/ local guidelines;

- Administer treatment: second dose of AZCQ will be administered at home under supervision by the fieldworker(s);
- Confirm that the LLINs has been installed in the home of the subject.

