9.2.1. Analysis of Primary Endpoint

The proportion of subjects with parasitological response (PCR corrected) at Day 28 post first dose of study medication will be estimated for the primary endpoint using the MITT and PP subject populations. The proportion will be estimated from the Kaplan-Meier curve based on the time to the first occurrence of parasitological failure (PCR corrected). Use of the Kaplan-Meier curve/product limit estimator is recommended by WHO⁸ and has been used in analyzing primary efficacy endpoints in late stage antimalarial treatment clinical trials.⁹²⁻⁹⁴

A subject will be a parasitological responder if she has a zero parasite count on the Day 7 visit without subsequent recrudescence (PCR corrected) through the day of consideration, otherwise she is a parasitological failure. In addition, subjects who withdraw from the study treatment during the first three days due to development of malaria symptoms and are administered antimalarial standard of care treatment for malaria in pregnancy, will be considered parasitological failures. The time (number of days) to the first occurrence of parasitological failure will be the analysis variable. The time in days is defined as [date of the parasitological failure event – date of the first dose of study medication + 1].

Subjects who do not experience the defined event (parasitological failure) will be censored as follows:

- Subjects who withdraw from the study early due to any reason will be censored on the day of the last available blood smear measurement;
- Subjects who continue on in the study but have all remaining blood smears missing from a given point in time onward will be censored on the day of the last available smear;
- Subjects completing the Day 42 visit post first dose of study medication will be censored on the day of the last available blood smear measurement;
- Subjects receiving any concomitant antimalarial for reinfection (PCR corrected) or in the absence of parasitemia will be censored at the visit date if the antimalarial is given after collection of the blood smear on that day. Otherwise the subject will be censored on the day of the last available previous blood smear measurement;
- Subjects who are lost to follow-up without any follow-up blood smears will have a censored duration of 1 day.

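### The per-protocol definition drops women whose dosing was stopped for malaria symptoms, although the plan counts them as failures, so the PP estimate can only be pushed upwards

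*Protocol*

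**What the plan says.** Four rules in the protocol meet on this point.

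- **PP definition (Section 9.2).** "PP is a subset of MITT subjects who receive all 3 days of study medication". No exception is made for a course cut short by failure.
- **Dosing rule (Sections 6.1.2 and 6.1.3).** A woman who presents with symptoms of malaria on Day 1 is handled as follows: "no further AZCQ dose would be given. The subject would be immediately referred to the investigator for parasite counts and appropriate treatment for malaria". Section 6.1.3 repeats the rule for Day 2. In both lists it stands ahead of that day's dose.
- **Failure rule (Section 9.2.1).** The rule covers "subjects who withdraw from the study treatment during the first three days due to development of malaria symptoms" and continues: "and are administered antimalarial standard of care treatment for malaria in pregnancy, will be considered parasitological failures". The other route to failure runs through the smears: a woman is a responder only if "she has a zero parasite count on the Day 7 visit without subsequent recrudescence (PCR corrected) through the day of consideration".
- **Use of PP (Section 9.2.1).** The Day 28 proportion "will be estimated for the primary endpoint using the MITT and PP subject populations". Neither population is named as leading. Section 9.2.2 carries the same PP set into the secondary response endpoints.

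The sensitivity analyses in Section 9.2.1 count premature discontinuation as failure, and they too are run within MITT and PP.

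**The concern.** A per-protocol set is meant to remove women who departed from the protocol. Here it also removes women who followed the protocol exactly and failed. Their dosing stopped because the protocol told the staff to stop it, for the same event that Section 9.2.1 counts as failure. Membership of PP therefore depends on the outcome being estimated, and the resulting error runs in one direction only.

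At stake is how one of the two reported primary estimates is read. The study supports a regulatory dossier by describing how well a course clears parasites. A PP rate above the MITT rate would normally be taken as the gain from completing treatment. Part of that gap could simply be early failures that the PP definition cannot admit.

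**Working it through.** The protocol gives no PP figure and no rate of early symptomatic failure, so there is no planned number to reproduce. The check has two parts.

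**1. Tracing the rules**

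| Woman | Third dose taken? | Status under 9.2.1 | In PP? |
|---|---|---|---|
| Symptoms at Day 1 or Day 2 visit, before that day's dose; standard antimalarial given | No | Failure | Never |
| Symptoms as above, no antimalarial given | No | Not a failure by this rule | No |
| Three doses, positive smear on Day 7 | Yes | Failure | Yes |
| Three doses, later recrudescence | Yes | Failure | Yes |
| Stopped after repeat vomiting (5.3.3), for safety (6.2), or missed a dose | No | Not a failure on that ground | No |

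Only the first row is lost to PP because of outcome, and that loss is total. The sensitivity analysis in PP cannot recover these women, because they were removed before it starts.

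**2. Size**

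Inputs:
- Enrolment is about 166 (Section 9.1).
- Dropout is about 10% (Section 9.1), which leaves 166 × 0.90 ≈ 149.
- The planning response is 95% or more (Section 9.1). Five per cent of 149 is 7.45 and of 166 is 8.3; rounded up, F = 8 and F = 9 failures.
- k, the number of the F failures who were stopped for symptoms before the third dose, is an assumption. Values from 0 to 5 are shown.
- No other woman is assumed to be excluded from PP.

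Crude proportions:
- MITT = 1 − F/N
- PP as written = 1 − (F − k)/(N − k)
- Excess = PP − MITT = MITT × k/(N − k)

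Example, N = 149, F = 8, k = 3: MITT = 141/149 = 94.63%; PP = 141/146 = 96.58%; excess = 94.63 × 3/146 = 1.94 points.

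| k | N = 149, F = 8: MITT | PP | Excess (points) | N = 166, F = 9: MITT | PP | Excess (points) |
|---|---|---|---|---|---|---|
| 0 | 94.63% | 94.63% | 0 | 94.58% | 94.58% | 0 |
| 1 | 94.63% | 95.27% | 0.64 | 94.58% | 95.15% | 0.57 |
| 3 | 94.63% | 96.58% | 1.94 | 94.58% | 96.32% | 1.74 |
| 5 | 94.63% | 97.92% | 3.29 | 94.58% | 97.52% | 2.94 |

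If these women stayed in PP as failures, PP would equal MITT in every row.

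The plan uses Kaplan-Meier rather than a crude proportion, but the mechanism is the same. These failures fall on Days 1 and 2, before the first scheduled follow-up smear on Day 7. With n women at risk then, MITT = (1 − k/n) × PP, other things equal. Women lost without any follow-up smear are censored at 1 day and have already left the risk set; later dropouts are still in it. So n lies between roughly 149 and 166, the two cases shown.

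**The case against.** The case on the other side has real content.

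- **The unaffected estimate is always reported.** MITT is named first for the primary endpoint and keeps these women as failures. The synopsis adds an ITT analysis. No hypothesis is tested and no decision rule rests on PP. This limits the harm. It does not make an outcome-dependent exclusion sound in a population given equal standing for the primary endpoint.
- **A completers-only set answers a recognisable question.** The objective in Section 2.1 concerns a 3-day regimen, and the early-failure rule is triggered by symptoms, without itself requiring parasitaemia. Asking what a finished course achieves is legitimate as a supplement. As defined, however, PP describes women who were still free of symptoms when the third dose was due, which is a selected group rather than the enrolled population under full compliance.
- **k may be small or zero.** Women are asymptomatic at entry (Sections 4.1 and 4.2). Section 1.5.2.2 cites PCR-corrected Day 28 efficacy of 98% and 100% in symptomatic African adults; at 98%, 149 women would yield about 3 failures in total (0.02 × 149 = 2.98). With 8 or 9 failures, k = 5 means that more than half arise before the third dose. The upper rows of the table are therefore an outer illustration.

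Two stronger readings are tempting and are not supported. A reader might infer that PP removes every early failure. It does not: a woman who took three doses and has a positive Day 7 smear stays in PP, as does one whose symptoms begin after the third dose. A reader might also infer that any MITT-PP difference is an artefact. It is not: PP also loses women for repeat vomiting, safety withdrawal and missed doses, so the difference is a mixture.

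**Conclusion.** The point holds in a limited form. Women stopped for malaria symptoms before the third dose and then given standard treatment are failures by definition and are always outside PP. This biases the PP estimate of the primary endpoint upwards whenever such women exist. MITT and ITT are not affected.

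The size depends on a count that the protocol does not give. At about 94.6% MITT response, the PP excess is 0 if there are none, about 0.6 points for one, 1.7 to 1.9 for three and 2.9 to 3.3 for five, against a planned interval half width of at most 5 points. These figures rest on crude proportions, on 8 failures among 149 or 9 among 166, and on no other PP exclusions. The direction of the bias rests on none of them.

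**What to change.** In Section 9.2, define PP as MITT women who either completed the three-day course or took every dose due up to a protocol-defined parasitological failure. Symptom-stopped failures then remain in PP and count as failures. Women whose dosing ended for other reasons, such as repeat vomiting, safety withdrawal or a missed dose, stay outside PP as now. Section 9 says that major changes to the primary analysis will also be reflected in a protocol amendment, so the clause should go in the protocol and be carried into the analysis plan.

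The cost is one clause. The PP rate may come out slightly lower, and PP is no longer strictly a completers-only set; if that set is of interest, it can be reported as a labelled supplement. Dosing and stopping rules, visits, data collection and sample size are untouched.
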